6.2.9 Dose escalation

Dose escalation post-toxicity after cycle 2 (Day 29)

Patients who have experienced treatment-related \geq grade 3 toxicity of any nature aside from thrombocytopenia, or grade 4 thrombocytopenia may not dose re-escalate nor return to the dose level for which this toxicity was encountered.

At the discretion of the Investigator, a patient may undergo dose re-escalation if it is felt to be in the best interest of the patient, and they have met the criteria as outlined in Section 6.2.6, 6.2.7, or 6.2.8 depending on the toxicity. For patients who undergo dose re-escalation, platelet counts must be obtained at least weekly for 4 weeks, and then at least every second week for the next 4 weeks. Thereafter, they may resume monthly evaluations.

Patients may continue treatment with RUXOLITINIB and PANOBINOSTAT until they experience unacceptable toxicity that precludes any further treatment, disease progression, and/or at the discretion of the Investigator. Patients will be discontinued from the study if they withdraw consent, or if the treating physician judges that further therapy with RUXOLITINIB and PANOBINOSTAT is no longer in the patient's best interest.

6.2.9.1 Intra-patient dose escalation Post MTD and/or RPTD determination (non-toxicity related)

Intra-patient dose escalation may be permitted by the Investigator following 13 patients treated for at least 2 cycles at the RPTD. During the course of study treatment, patients can be dose-escalated to the next higher dose level only once every two cycles, provided that ALL of the following criteria are met:

- Inadequate efficacy is seen with the current dose level, as defined by the observation of one or both of the following:
 - Not achieving at least a 50% reduction in palpable spleen length compared to baseline
 - Lack of meaningful improvement in disease symptoms based on the Investigator's expert judgment
- No treatment related toxicity has occurred with the current dose level, resulting in treatment reduction or interruption or discontinuation in the previous 56 days
- The higher dose with which the patient is to be treated does not exceed the MTD and/or RPTD
- Platelet counts must be obtained at least weekly for 4 weeks, and then at least every second week for the next 4 weeks after escalation. Thereafter, they may resume monthly evaluations.

There is no limit to the number of times the study drug may be increased for each patient, provided the above rules are followed for each subsequent dose escalation. The same rules for dose reductions as outlined in Section 6.2.7 apply to these patients.

The rules for intra-patient dose escalation described above apply only to those patients who have undergone one and only one dose reduction. Once a patient undergoes a dose reduction due to treatment-related toxicity, the patient may not have a dose increase unless they have been on a stable dose for at least 28 days with no dose interruptions.

6.2.10 Optional dose tapering strategy for RUXOLITINIB in the event of discontinuation

When RUXOLITINIB therapy is stopped, the return of constitutional symptoms associated with elevated cytokines (e.g. night sweats, fever, fatigue) that had been suppressed while on therapy is expected. When a decision is made to permanently discontinue RUXOLITINIB therapy for reasons other than hematologic safety, a dose tapering strategy may be considered, based on evaluation of the condition of the patient, current dosing regimen and the clinical judgment of the Investigator, so that symptoms may return to pre-treatment condition more slowly. If considered to be medically necessary, the Investigator may use any treatment to manage withdrawal from RUXOLITINIB including gradual tapering of the study drug dosage or use of other medications to manage events occurring after discontinuation. Short-term course of corticosteroids at doses > 10mg/day have been used in patients with MF and may be considered as part of a tapering strategy. Corticosteroids may be started prior to, or concurrent with, RUXOLITINIB tapering. When a decision has been made to discontinue the patient utilizing a tapering strategy, regardless of the use of concomitant medications, safety data will

continue to be assessed in accordance with the protocol for a period of times at least through the continued administration of RUXOLITINIB and 30 days after for AEs.

6.2.11 Management of diarrhea

Patients should be instructed to contact their physician at the onset of diarrhea. Each patient should be instructed to have loperamide readily available and to begin treatment for diarrhea at the first episode of poorly formed or loose stools or the earliest onset of bowel movements more frequent than normally expected for the patient.

Loperamide 4 mg should be taken at the first loose stool or more frequent than usual bowel movements, followed by 2 mg as needed, no more frequently than every 4 hours, not to exceed a total of 16 mg in 24 hours. Patients with diarrhea grade 2 despite this loperamide regimen should interrupt study treatment as described in Table 6.2.3. If the above regimen is inadequate then additional evaluation and treatment should be pursued as medically indicated. Replacement i.v. fluids and electrolytes may be used as appropriate. Additional treatment should be provided in accordance with institutional standard of care and/or local guidelines.

Premedication with loperamide is not recommended.

The use of drugs with laxative properties should be avoided because of the potential for exacerbation of diarrhea. Patients should be advised to contact their physician to discuss any laxative use.

6.3 Concomitant medications

6.3.1 Permitted concomitant therapy

The patient must be told to notify the investigational site about any new medications he/she takes after the start of the study drug. All medications (other than study drug) and significant non-drug therapies (including physical therapy and blood transfusions) administered during the study must be recorded in source documents and eCRFs.

6.3.2 Permitted concomitant therapy requiring caution and/or action

The following medications have restrictions on use or doses or required changes to the way in which RUXOLITINIB and/or PANOBINOSTAT is administered during the study:

- Systemic corticosteroid doses greater than the equivalent of 10 mg of prednisolone per day are not permitted, unless use is part of a RUXOLITINIB dose tapering strategy (Section 6.2.10) as this may impact splenic size and cytokine reduction and interfere with the ability to assess the clinical activity of this combination of agents in this patient population.
- In patients for whom low molecular weight heparin use will be initiated, the degree of thrombocytopenia should be considered, coagulation parameters monitored, and dose of anti-coagulant adjusted accordingly.
- During the study, concomitant use of strong CYP3A4/5 inhibitors is strongly discouraged. However, when such a concomitant administration of a strong systemic CYP3A4 inhibitor (see Appendix 1 for a listing of these medications) is required for patient management, the

dose of RUXOLITINIB must be adjusted as described in Section 6.3.4. However, there is no dose adjustment of PANOBINOSTAT proposed.

- During the study, the use of moderate CYP3A4 inducers (e.g. bosentan, efavirenz, etravirine, modafinil, nafcillin, ritonavir, talviraline, tipranavir) is discouraged, and investigators should seek alternatives where possible. No dose adjustments are needed when moderate CYP3A4 inducers are co-administered with study treatment. However, any concomitant use of moderate CYP3A4 inducers must be documented. See Appendix 1 for a listing of these medications.
- During the study, concomitant use of medications which are known CYP2D6 substrates are to be used with caution. See Appendix 1 for a list of these medications.
- Granulocyte growth factors (G-CSF) are not allowed while study medication is being administered but may be used for severe neutropenia at the Investigator's discretion while study medication is being withheld.

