4. Other concurrent severe and/or uncontrolled medical conditions (e.g., uncontrolled diabetes or active or uncontrolled infection) including abnormal laboratory values, that could cause unacceptable safety risks or compromise compliance with the protocol
5. Patients using medications that have a relative risk of prolonging the QT interval or inducing torsade de pointes if treatment cannot be discontinued or switched to a different medication prior to starting study drug
6. Concomitant use of strong CYP3A4 inhibitors
7. Patients who have received targeted agents within 2 weeks or within 5 half-lives of the agent and active metabolites (whichever is longer) and who have not recovered from side effects of those therapies.
8. Chemotherapy within 3 weeks prior to screening are excluded (other than hydroxyurea at stable doses and will be discontinued 24 hours prior to starting study drug).
9. Patients with an active bleeding tendency or are receiving any treatment with therapeutic doses of sodium warfarin (Coumadin[®]) or coumadin derivatives. Patients will be allowed to enter study on aspirin at doses of 81mg/d.
10. Patients who have undergone major surgery≤ 4 weeks prior to starting study drug or who have not recovered from side effects of such therapy
11. Women who are pregnant or breast-feeding or women of childbearing potential (WOCBP) not using an effective method of birth control. WOCBP are defined as sexually mature women who have not undergone a hysterectomy or who have not been naturally postmenopausal for at least 12 consecutive months (i.e., who has had menses any time in the preceding 12 consecutive months). Women of childbearing potential must have a negative serum pregnancy test within 24hrs of receiving the first dose of study medication.
12. Male patients whose sexual partners are WOCBP not using effective birth control
13. Patients with a prior malignancy within the last 5 years (except for basal or squamous cell carcinoma, or *in situ* cancer of the cervix)
14. Disease associated with secondary MF such as metastatic carcinoma, lymphoma, myelodysplasia, hairy cell leukemia, mast cell disease or acute leukemia (including M7 disease or acute panmyelosis with MF)

6 Treatment

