Miscellaneous drugs 
• arsenic trioxide• bepridil• cisapride• levomethadyl• methadone

*Note: azithromycin, ciprofloxacin, levofloxacin, pefloxacin, ofloxacin, tosufloxacin, difloxacin, temafloxacin, fleroxacin, acrosoxacin, nalidixic acid and enoxacin are allowed.

[^]Intravenous dolasetron is contraindicated for preventing nausea and vomiting associated with chemotherapy based on FDA drug safety communication dated December 17, 2010. Based on this finding, both intravenous and oral dolasetron are prohibited to be taken with PANOBINOSTAT.

This is not a comprehensive list of medications which may prolong the QT interval and/or induce Torsades de pointes. This list of medications was developed in collaboration with an external cardiology consultant, and represents those medications which are deemed to have an unacceptable risk of co-administration with PANOBINOSTAT.

The following website may be referenced as a supplemental guide for drugs which have been associated with Torsades de pointes or prolonging the QT interval but at this point lack substantial evidence for causing Torsades de pointes:

<http://www.azcert.org/medical-pros/drug-lists/drug-lists.cfm> (Version 3/25/2008).

Medications listed on the website which do not appear in [Table 2-1](#) above may be used with caution at the discretion of the investigators.

Ondansetron (a known CYP2D6 substrate, see [Table 4-1](#)) has been associated with Torsades de points and QT prolongation but has not been shown to cause Torsades de pointes. Therefore, ondansetron is not per se prohibited to be combined with PANOBINOSTAT but caution is to be exercised and close monitoring for signs and symptoms of QT prolongation is recommended.

C. Medications which are known strong CYP3A4/5 inhibitors to be used with caution

The use of these drugs is prohibited during the first cycle of study treatment

PANOBINOSTAT is a substrate of CYP3A4 with minor involvement of CYP2D6, and CYP2C19 in *in vitro* evaluation of its metabolism. Thus, a clinical drug-drug interaction study was conducted using ketoconazole, a strong CYP3A inhibitor, in combination with PANOBINOSTAT in study [\[CLBH589B2110\]](#).

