Multiple ketoconazole doses at 400 mg increased C_{max} and AUC of PANOBINOSTAT by 1.6- and 1.8-fold, respectively, but with no change in T_{max} or half-lives in 14 cancer patients. The less than 2-fold increase in PANOBINOSTAT AUC upon co-administration of a strong CYP3A inhibitor is considered a weak drug inhibition and not clinically relevant, as PANOBINOSTAT doses at least 2-fold greater than the evaluated 20 mg dose (i.e., 40 mg and 60 mg) have been safely administered in patients. Thus, co-administration of PANOBINOSTAT with a moderate or weak CYP3A inhibitor is allowed. However, clinical monitoring of signs and symptoms of PANOBINOSTAT treatment related adverse events is recommended when long-term (≥ 1 week) concomitant administration of any strong CYP3A inhibitors and PANOBINOSTAT is medically indicated or investigated in a clinical study.

RUXOLITINIB is metabolized in the liver predominantly by the CYP3A4 isozyme. With concomitant dosing of potent CYP3A4 inhibitors such as those medications listed in [Table 3-1](#), plasma exposure of RUXOLITINIB increases approximately 2-fold. Use of those medications listed in [Table 3-1](#) is strongly discouraged, and investigators should consider alternative therapies wherever possible. However, if the use of a potent CYP3A4 inhibitor is necessary for the sake of the patient's safety, then a dose reduction of ~50% of RUXOLITINIB is mandatory. See [Section 6.3.4](#) for further details of this dose reduction schema.

Based on the low overall bioavailability of topical ketoconazole, with very low systemic levels seen following topical administration, no dose adjustment of RUXOLITINIB is needed for use with topical ketoconazole. No dose adjustments are necessary when RUXOLITINIB is co-administered with erythromycin, or by extension, with other moderate or weak inhibitors of CYP3A4, including grapefruit juice.

Patients with impaired liver function (as defined by NCI CTEP criteria)¹ are recommended not to receive PANOBINOSTAT concomitantly with strong CYP3A inhibitors because potential interaction has not been established in this population.

Table 3-1 Medications which are known strong CYP3A4/5 inhibitors to be used with caution

Macrolide antibiotics*
• telithromycin
• troleandomycin
Antifungals (azoles)
• ketoconazole
• itraconazole
• posaconazole
• voriconazole
Antidepressants
• nefazodone
HIV protease inhibitors:
• indinavir
• nelfinavir
• ritonavir
• saquinavir
• lopinavir
Miscellaneous drugs or products

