clomipramine	mexiletine
desipramine	flecainide
imipramine	Others (listed below):
fluoxetine	codeine
paroxetine	dextromethorphan
venlafaxine	tamoxifen
duloxetine	tramadol
Antiemetics (listed below):	
ondansetron [^]	

[^]Intravenous dolasetron is a CYP2D6 substrate and contraindicated for preventing nausea and vomiting associated with chemotherapy based on FDA drug safety communication dated December 17, 2010. Please see [Table 2-1](#).

This is not a comprehensive list of CYP2D6 substrates. Additional updated versions of this list, which are meant to be used as a guide, may be found at the following website: <http://medicine.iupui.edu/clinpharm/DDIs/ClinicalTable.asp>

E. Medications which are known to be moderate inducers of CYP3A4 are to be used with caution

During the study, the use of moderate CYP3A4 inducers (e.g. bosentan, efavirenz, etravirine, modafinil, nafcillin, ritonavir, talviraline, tipranavir) is discouraged, and investigators should seek alternatives where possible. No dose adjustment will be used when moderate CYP3A4 inducers are co-administered with RUXOLITINIB. However, any concomitant use of moderate CYP3A4 inducers must be documented.

This is not a comprehensive list of medications which may induce CYP3A4/5. The above list was compiled by using information listed under “draft guidance for industry, drug interaction studies, CDER 2006”, Indiana University School of Medicine drug interaction tables at <http://medicine.iupui.edu/clinpharm/DDIs/ClinicalTable.asp>, and “drug interaction database” from University of Washington.

References (available upon request)

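### Ritonavir is listed both as a moderate CYP3A4 inducer (no dose change) and as a strong CYP3A4/5 inhibitor (ruxolitinib halved), and nothing says which listing governs

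*Combined protocol and SAP*

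**What the plan says.** **As an inducer.** Section 6.3.2 states that "the use of moderate CYP3A4 inducers (e.g. bosentan, efavirenz, etravirine, modafinil, nafcillin, ritonavir, talviraline, tipranavir) is discouraged". It adds: "No dose adjustments are needed when moderate CYP3A4 inducers are co-administered with study treatment". Use must be documented. Appendix 1 part E gives the same list of drugs, ritonavir included, and says: "No dose adjustment will be used when moderate CYP3A4 inducers are co-administered with RUXOLITINIB".

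**As a strong inhibitor.** In Appendix 1 part C, ritonavir appears under HIV protease inhibitors in "Table 3-1 Medications which are known strong CYP3A4/5 inhibitors to be used with caution". Four rules attach to that class:

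- Exclusion criterion 6 (Section 5.2) bars "Concomitant use of strong CYP3A4 inhibitors", and Section 6.3.4 repeats the bar on enrolment.
- Part C says: "The use of these drugs is prohibited during the first cycle of study treatment". Section 6.3.4 agrees.
- If such a drug is needed later, part C says "then a dose reduction of ~50% of RUXOLITINIB is mandatory". Section 6.3.4 gives the steps: 5, 10 or 15 mg BID becomes the same tablet dose once daily.
- The strong-inhibitor bullet of Section 6.3.2 says that the "dose of RUXOLITINIB must be adjusted as described in Section 6.3.4".

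**The concern.** One drug falls under two rules that cannot both be followed. An investigator who relies on the inducer bullet breaches the plan's own mandatory dose cut, and possibly its entry and Cycle 1 rules, while following an instruction that the plan also gives.

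The body of the protocol makes this the easier path. Section 6 names ritonavir only as an inducer, and the examples of strong inhibitors in 6.3.4 do not include it. The pointers from 6.3.2 to Appendix 1 do not resolve the matter, because Appendix 1 contains both listings. No exclusion criterion names HIV infection, so a ritonavir user's eligibility under criterion 6 turns on how the drug is classed.

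The stake is ruxolitinib exposure in a combination for which Section 1.4.2 already expects thrombocytopenia to be dose-limiting.

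**Working it through.** **Step 1. Set the rules side by side for a patient on ritonavir.**

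| Question | Inducer listing (6.3.2; Appendix 1 part E) | Strong-inhibitor listing (Table 3-1; criterion 6; 6.3.4) |
|---|---|---|
| Entry | not barred | barred |
| Cycle 1 | discouraged, documented | prohibited |
| After Cycle 1 | discouraged, documented | strongly discouraged; only if needed for the patient's safety |
| Ruxolitinib, assigned 5 mg BID | 5 × 2 = 10 mg/day | 5 × 1 = 5 mg/day |
| Ruxolitinib, assigned 10 mg BID | 10 × 2 = 20 mg/day | 10 × 1 = 10 mg/day |
| Ruxolitinib, assigned 15 mg BID | 15 × 2 = 30 mg/day | 15 × 1 = 15 mg/day |

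The daily dose differs by a factor of 2 in each dosing row.

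**Step 2. Look for a precedence rule.** None is stated in 6.2.7, 6.3.1 to 6.3.4, or Appendix 1. The notes under Table 3-1 cover azithromycin, orange juice and clarithromycin. The clarithromycin note is instructive: that drug also belongs to two classes, and the authors say which table handles it. Ritonavir has no such note.

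**Step 3. Translate a missed adjustment into exposure.** Inputs:

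- Strong inhibitors raise ruxolitinib exposure about 2-fold (6.3.4; Appendix 1 part C).
- Exposure is linear in dose (1.3.4).
- The single-agent ruxolitinib MTD is 25 mg BID (Table 1-4, footnote a).
- The single-agent titration range is 10–25 mg BID (1.3.1).

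Equivalent dose = assigned dose × 2; share of MTD = equivalent dose / 25.

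- 10 mg BID: 10/25 = 40% as assigned. Unadjusted with a strong inhibitor, 10 × 2 = 20 mg BID and 20/25 = 80%, inside the 10–25 mg range.
- 15 mg BID: 15/25 = 60% as assigned. Unadjusted, 15 × 2 = 30 mg BID and 30/25 = 120%, outside the range.

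With the 6.3.4 cut, 10 mg once daily × 2 = 20 mg/day, the equivalent of 10 mg BID, and 15 mg once daily × 2 = 30 mg/day, the equivalent of 15 mg BID. The cut therefore offsets the interaction.

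**Step 4. Check the opposite error.** Suppose ritonavir were a net inducer in some patient and the dose were halved. The documents give no induction figure for ritonavir. As an assumption, take a fall in exposure of 0% to 70%, the 70% being the rifampin figure in 1.3.4, used as an outer bound. Exposure relative to the assigned dose is 0.5 × 1.00 = 50% down to 0.5 × 0.30 = 15%.

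**The case against.** The best case against is that the conflict is unlikely to do harm. The strong-inhibitor rule is stated several times and as mandatory: in 6.2.7, 6.3.2, 6.3.4 and Appendix 1 part C. The strong-inhibitor bullet in 6.3.2 sends the reader to an appendix table that names ritonavir. Appendix 1 part B stresses avoiding Table 3-1 drugs with panobinostat and requires that any such use be discussed with the sponsor. Patients must report new medicines (6.3.1), the diaries tell them to start none without their physician's approval, and the investigators approve each patient's eligibility (7.1.2.1). A careful investigator would probably take the more cautious rule. Blood counts are reviewed before dosing (7.2.5), and 1.3.3 describes ruxolitinib thrombocytopenia as mostly reversible with interruption or reduction.

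All of this stands and lowers the likelihood and consequence of an error. None of it says which listing governs. The sponsor discussion, for instance, is triggered only if the reader already treats ritonavir as a Table 3-1 drug.

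Three stronger readings are tempting and are not supported:

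- A reader might infer that the listings give opposite instructions. They do not: one leaves the dose unchanged and the other halves it.
- A reader might infer that the safety margin in 6.2.1 is lost throughout. That margin concerns starting doses below 50% of the MTD. It applies at 10 mg BID (40%) and would be lost there, but 15 mg BID is already at 60% by design.
- A reader might infer a predictable rise in severe thrombocytopenia. The single-agent grade 3/4 rates in 1.3.3 were 6/30 (20%) at 10 mg BID, 1/35 (3%) at 15 mg BID and 17/47 (36%) at 25 mg BID. They do not rise steadily, and 1.3.3 attributes the 10 mg figure partly to lower baseline platelets. They are context only, not a dose-effect estimate.

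**Conclusion.** The inconsistency is real and is in the current text. For a patient on ritonavir it leaves a 2-fold difference in daily ruxolitinib dose, and conflicting answers on entry and Cycle 1 use, with no rule to choose between them. If the dose is left alone and ritonavir acts as Table 3-1 classes it, exposure is equivalent to about 80% of the single-agent MTD at 10 mg BID and about 120% at 15 mg BID.

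Those figures assume that the plan's 2-fold value for strong inhibitors applies to ritonavir and that exposure is proportional to dose. They use a single-agent MTD, not one for the combination. The documents do not say how many patients might take ritonavir; few seems likely. No endpoint, sample size or error rate depends on the point. It is a low-severity safety inconsistency in the drug lists.

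**What to change.** Add one sentence to Section 6.3.2 and to Appendix 1 part E: any drug in Table 3-1 is handled under the strong-inhibitor rules (exclusion criterion 6 and Section 6.3.4), even if it is also listed as an inducer.

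Simply deleting ritonavir from the inducer lists would be a firmer pharmacological claim than the documents support, since they do not show which effect on ruxolitinib predominates. A precedence rule needs no such claim; it chooses the more cautious instruction.

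The cost is one sentence in two places, with no new data, visits or patients. A ritonavir user would be kept out at entry, as criterion 6 already requires for strong inhibitors. The downside is under-exposure if ritonavir were a net inducer in a given patient: about 15–50% of the assigned exposure on the assumption above. Section 6.3.4 restores the prior dose only once the inhibitor course is complete, so the shortfall would last as long as ritonavir does, which may not be short.
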